7.0 REGISTRATION GUIDELINES

7.1 Registration Timing

Patients must be registered by the start time of the first intervention session.

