7.2.2 Randomization

Patients who meet eligibility criteria will be approached to enroll in the randomized telehealth intervention versus a usual care comparison group using an approved consent process (see Schema). **Consents will need to be signed and received prior to randomization.**

Subjects will be randomized using stratified permuted block randomization. Once consented, the participant will be randomized to OSMT or UC, using computer-generated random lists blocked by site and gender, and with assigned arm in sealed envelopes blind to investigators and coordinators until assignment. This means that each participating site will have a unique pair of computer-generated randomization lists, one for male and the other for female, ensuring balance by sex between intervention and usual care groups at each site without the need for communication with a data coordinating center core for each randomization. The randomization lists will be comprised of blocks of 4 with permuted patterns so that balance is achieved after multiples of 4 in each sex have been randomized.

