7.2.3 Consent

Participant Consent – Potential participants will be afforded sufficient time to consider whether or not to participate in this research study. If the ostomate agrees, informed consent will be obtained. If patients wish to have more time prior to signing the consent, they may mail back the consent. For potential participants contacted over the phone, the same information will be relayed, and they will be asked to mail the consent prior to randomization. Participants will complete the baseline assessment following informed consent.

Caregiver Consent – Participants will designate their caregivers upon registration. It can be anyone they feel they want in that role for this study. As with participants, caregivers will need to have signed a consent prior to participation. Only some basic information will be obtained for caregivers, including age, gender, relationship, and current work status. This will be maintained in a study sheet for every patient. Appendix 11

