8.1 Session Information/Preparation

Site coordinators at the three accrual sites will communicate to each other the number of subjects being assigned to a group as they are randomized to the Intervention arm. When the group enrollment gets to six, they will close enrollment to that group and begin enrolling in the next group. Coordinators will slow enrollment if needed so that subjects are not enrolled in a group starting more than 2 months from the enrollment date. If needed, the team will discuss adding additional groups to the schedule on different dates so that subjects will be able to start within the 2-month window from enrollment date.

For intervention session schedules, the protocol will include two different schedules for intervention session administration. This design is to provide flexibility for participants and also to maximize study accrual and participation. The schedules include:

Schedule #1: Two sessions administered on the same day, with a break in between. There will be a 4-week interval between the first set of 2 sessions and second set of 2 sessions. The caregiver session will be held two weeks after the first set of sessions.

Schedule #2: One session administered per day, once a week over a five-week period. There will be a one-week interval between session 2 and session 3 during which the caregiver session will be held.

The two schedules vary throughout the study period based on participants' convenience and preference.

If a subject misses a session, they can make up just the missed session with the next 1 or 2 scheduled groups rather than start over with a new group. If they miss both Session 1 and Session 2, they can be re-assigned to the next group as long as the next group size doesn't

exceed 6, or at the ostomy nurses' ([name] and [name]) discretion if the group size would exceed 6.

If a subject misses Session 3 or Session 4 or both, they can make up the missed session(s) with the next 1 or 2 scheduled groups. If they miss both chances to make up the sessions, they will be asked to do the surveys and will be analyzed as a separate group using an intent-to-treat contrast.

To account for making up sessions or delays in completing interim surveys, for both intervention and usual care groups, the 6-month followup surveys will be requested from subjects 6 months after the date the interim surveys are completed.

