8.1.1 Telehealth Connection Information (Appendix 8)

8.1.2 Group Rules (Appendix 9)

8.1.3 Goal Setting (Appendix 10)

Participants will receive the four-page goal setting form (Appendix 10) as part of the patient packet mailed to them before the first session, and will be asked to list goals for helping improve their daily life prior to Session 1 (page 1 of the form). Their goals will be discussed during Session 1 and will be revisited and possibly revised in Session 2 (page 2 of the form) and again in Session 3 (page 3 of the form). Participants should be instructed to keep a copy of the first page of the form and return the completed first page with the baseline surveys. Participants should be instructed to return page 2 after Session 2, and return page 3 after Session 4 along with the interim surveys. The final page 4 should be returned with the followup surveys six months after the end of the sessions. Site Coordinators will key in goal setting data for data entry.

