15.0 APPENDICES

15.1 Appendix 1 Curriculum

Session 1 - Introduction (5 min., Session 1, Ostomate folder)

You are here to participate in an intervention to help in caring for and coping with your ostomy. We want to remind everyone that participation is completely voluntary and you may withdraw at any time. The sessions are confidential; only first names will be used. Please respect the privacy of others. Please do not, by any means or technology, photograph, video record, or audio record any portion of the OSMT Zoom video conferencing sessions. If you are disruptive to others, we will ask you to no longer participate. In your packet, there is a participant's agreement on conduct. Please only one person speak at a time and allow others to talk; everyone will have a chance to share with the group. If you are disruptive during the session, you may be asked to leave that session. Remember, you can contact your local Peer Ostomate outside the sessions if you need additional assistance. In the interest of safety, we must remind everyone not to join the video conferencing sessions while driving.

We also would like to do a quick roll call. Again, we will be using only first names. Please also tell us what kind of device you are using (e.g. iPad, Apple PC, iPhone, etc.).

Before we begin, did everyone fill out the surveys either electronically or mailed? If the surveys were mailed to you, were they mailed back?

Next, please refer to the page in your packet related to instructions for the telehealth connection. If you are using a smartphone or iPad, please make sure they are charged or plugged in, as these sessions use a lot of energy. Please mute your phone, and remember to unmute if you want to speak. To mute/unmute on a PC/laptop, move the cursor to the lower left corner of your screen until the controls appear in a bar at the bottom, then click on the microphone icon to toggle on/off; on a smartphone or iPad, touch the screen to make the controls appear and touch the microphone to toggle on/off. We encourage participation from everyone. If you are on a phone, you can use your finger to scroll over to see different participants; on a PC/laptop you can see all

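### No readable passage requires the baseline surveys to be finished before randomization, so the between-arm baseline-to-post comparison is open to bias

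*Protocol*

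**What the plan says.** **Order of events.** Protocol 7.2.2 states one precondition for opening the envelope: "Consents will need to be signed and received prior to randomization". It continues: "Once consented, the participant will be randomized to OSMT or UC". Section 7.2.3 adds: "Participants will complete the baseline assessment following informed consent". Both steps follow consent, and neither is ordered against the other. Section 9.5 gives no baseline date; it refers to 8.1, which deals with session scheduling and preparation.

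**The baseline packet.** Section 8.2.1 lists seven baseline items: COH-QOL-CRC, HADS, PAM, self-efficacy, ostomy knowledge, burden of care, and page 1 of the Goal Setting form. Section 8.1.3 says that this form arrives "as part of the patient packet mailed to them before the first session", and that participants are to "return the completed first page with the baseline surveys". In Appendix 10, page 1 is to be kept for discussion in Session 1 and has a field for the intervention nurse.

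**Session 1.** The script in Appendix 1 asks the OSMT group "Before we begin, did everyone fill out the surveys either electronically or mailed", and then whether mailed surveys have been sent back. Its assignments part says that the first survey packet contained the goal sheet.

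**Time available.** Under 7.1, "Patients must be registered by the start time of the first intervention session". Under 8.1, coordinators slow accrual so that "subjects are not enrolled in a group starting more than 2 months from the enrollment date". Section 8.2.6 has non-respondents telephoned after 2 weeks and sets no cut-off tied to allocation or to Session 1.

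**Use of baseline.** Protocol 12.2 and the SAP (Aim 1) name PAM as the primary outcome and assess the training effect from baseline to post. The power model in 12.13 is adjusted for baseline. The blinding described in 12.11 covers the assessment team before assignment, not participants.

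**The concern.** A baseline measure is protected by randomization only if it is fixed before the participant knows the arm. Here participants cannot be blinded and PAM is a self-report. Someone who knows that training is coming, or that it is not, may answer differently about confidence and readiness to act. If that happens in one arm, or in the two arms to different degrees, the baseline means differ for a reason other than chance, and the analysis treats the difference as a real starting point.

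What is at stake is the between-arm improvement in PAM (hypothesis 1.1.1), together with any model that adjusts for baseline. Self-efficacy, quality of life, knowledge and HADS come from the same survey set, and HADS is also a candidate covariate in 12.2. A lower OSMT baseline inflates the apparent benefit; a higher one hides it.

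**Working it through.** **1. What the text requires.** Set side by side, 7.2.2 gives consent then randomization, and 7.2.3 gives consent then baseline. Baseline first and envelope first both comply. The goal form points towards completion after allocation: it belongs to the baseline set, is returned with it, travels in a packet tied to Session 1, and names an intervention nurse. The Session 1 question shows that survey return is still being checked after allocation. No rule says what happens if the answer is no.

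**2. The plan's own scale.** Inputs from 12.13: PAM SD 13, correlation 0.60, alpha 0.05 (two-sided assumed), power 80%, 75 per arm, adjusted for baseline, two follow-ups.

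- Detectable difference = (1.960 + 0.842) × SD × √(2f/n).
- With f = (1 − 0.60²)/2 = 0.32, SE = 13 × √(0.64/75) = 1.20, and 2.80 × 1.20 = 3.36 (3.39 with t quantiles). The stated figure is 3.4, so it reproduces.

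**3. Bias.** Let d be the shift in the OSMT arm's mean baseline caused by knowing the arm, and p the share of that shift still present at post. The documents give neither, so both are assumptions. At arm level, d is the share completing late times the average shift per person: if a quarter complete late and shift by 4 points, d = 1. With equal SDs, the regression slope on baseline is the correlation, 0.60.

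- Change contrast: estimate = true effect − (1 − p)d.
- Baseline-adjusted: estimate = true effect − (0.60 − p)d.

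With p = 0, the bias sizes are:

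| d | Baseline-adjusted (0.6d) | As share of 3.4 | Change (d) | As share of 3.4 |
|---|---|---|---|---|
| 0.5 | 0.3 | 9% | 0.5 | 15% |
| 1 | 0.6 | 18% | 1.0 | 29% |
| 2 | 1.2 | 35% | 2.0 | 59% |

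**4. False-positive rate with no true effect, p = 0, 75 per arm.** Rate = Φ(b/SE − 1.96) + Φ(−b/SE − 1.96), where b is the bias. SE is 1.20 for the adjusted analysis. For the baseline-to-post change it is 13 × √(2 × 0.8/75) = 1.90, with 0.8 = 2(1 − 0.60).

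| d | Adjusted | Change |
|---|---|---|
| 0.5 | 5.7% | 5.8% |
| 1 | 7.9% | 8.2% |
| 2 | 17.0% | 18.4% |

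The SE of 1.20 treats the two follow-ups as independent given baseline. With correlation 0.60 among all three measures, f = (1 + 0.60)/2 − 0.60² = 0.44 and SE = 1.41; the adjusted rates become 5.5%, 7.1% and 13.6%.

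**5. Persistence.** With d = 2 and p = 0.5, the change bias falls to 1.0 and the adjusted bias to 0.2. With p = 1, the change bias is 0 and the adjusted bias is 0.8 in the opposite direction, still below 1.2.

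**The case against.** The strongest reply is that the order is unspecified, not wrong. A site that collects baseline at consent and then opens the envelope follows every readable sentence. The Session 1 question is in the past tense and may be a last check on surveys done weeks earlier; the assignments text also speaks of the first survey packet as already completed. Section 8.1.3 does not say that the packet is mailed after allocation, and 8.2.1 does not limit the goal page to OSMT. Section 7.2.2 refers to the Schema, which is not reproduced and may settle the order.

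All of that stands. A reader might infer that the documents put baseline after allocation; they do not say so. But an unstated order is not a safeguard, and the goal-form and Session 1 passages make late completion a realistic outcome.

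A reader might also infer that every primary contrast is affected. It is not. The sustained-effect contrast runs from post to follow-up and does not use baseline as an endpoint. The attendance analysis (1.1.3) lies within OSMT, where everyone knows the arm. Nor do the documents show that completion rates differ by arm: both arms receive the same $50 for the initial survey (7.2.5), and the two-week call is not arm-specific.

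On size, the shift is assumed, and participants still know their arm at post, so part of it may persist and reduce the bias. Any reporting bias at post is a separate problem that earlier baseline collection does not cure. Against the clinical-importance indices in 12.13 (6.5 and 8.0 points), a bias of 0.3 to 2 points is about 4% to 31%.

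**Conclusion.** The point holds in limited form. The readable text allows self-reported baseline PAM to be collected after the arm is known, and several passages suggest that this happens for at least some OSMT participants. The exposed analyses are the between-arm baseline-to-post contrast (hypothesis 1.1.1) and any baseline-adjusted model.

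Size and direction are unknown. For an assumed arm-level shift of 0.5 to 2 PAM points that is absent at post, the bias is about 0.3 to 1.2 points with adjustment (correlation 0.60) or 0.5 to 2 points on change, against the stated 3.4 at 75 per arm. At the low end the false-positive rate barely moves from 5%; at the high end it is roughly 14% to 18%. These are upper figures for each shift, since persistence to post reduces the bias. The conclusion would fall away if the Schema requires baseline before randomization.

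**What to change.** - In 7.2.2 and 7.2.3, require the coordinator to log the baseline PAM, self-efficacy, COH-QOL-CRC, HADS, knowledge and burden surveys as complete before the envelope is opened, in both arms. Record the survey and randomization dates.
- Settle the place of Goal Setting page 1: either collect it with those surveys before allocation, or drop it from the 8.2.1 baseline list and send it with the session packet. Align 8.1.3, Appendix 10 and the Session 1 script with the choice.
- For participants already randomized, compare survey and randomization dates, and pre-specify in the SAP a sensitivity analysis that flags or excludes baselines dated after allocation.

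The cost is a procedural amendment, one logging step, and a short delay between consent and allocation for those who use mailed surveys. If baseline is locked before the arm is disclosed, the expected shift from knowing the arm is zero and this source of bias is removed.

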15.2 Appendix 2a COH-QOL-CRC (full survey)

Survey: City of Hope Quality of Life baseline questions

Subject ID

Today's Date (month/day/year) / /

Ostomy Location/Care/Pre-Op

[figure not shown]
1. What kind of ostomy do you have?

- Colostomy
- Ileostomy
- Urostomy
- Don't Know

2. If you have a urinary ostomy, please skip this question. If you have an ileostomy or colostomy, was it supposed to be permanent or temporary?

- Permanent
- Temporary
- Don't Know

3. Please mark with an X on the figure of an abdomen the location of your ostomy?

3b. Please choose one of the following to describe the location of your ostomy?

- Lower Left Side;
- Lower Right Side;
- Upper Left Side;
- Upper Right Side

4. Does the location of your ostomy cause problem with clothing?

- Yes; No

5. Does this location of your ostomy cause you other problems? (if yes, please explain below)

6. Have you changed the style of clothing you wear because of your ostomy?

- Yes; No

7. Was your abdomen marked for the ostomy site before your surgery?

- Yes; No Don't remember

8. Did a nurse specialist (ostomy nurse) or physician explain your ostomy prior to your surgery?

- Yes; No Don't remember

9. Did a nurse specialist (ostomy nurse) help you learn to care for your ostomy after your surgery?

- Yes; No Don't remember

Sexual Activity

10. Were you sexually active before getting your ostomy?

- Yes; No

11. Have you been sexual activity since having your ostomy?

- Yes; No

12. Are you currently sexually active?

Yes; No

12b. If you ARE NOT currently sexual active, are you fearful of resuming sexual activity?

Yes; No

12c. If you ARE NOT currently sexual active, is that a problem for you?

Yes; No

12d. If you ARE currently sexual active, is there fear or anxiety associated with sexual activity?

Yes; No

12e. If you ARE currently sexual active, is your sexual activity satisfying?

Yes; No

13. Is undressing in front of your partner after your Ostomy a problem?

- Not a problem,
- A little problem,
- Somewhat a problem,
- Very much a problem,
- NA

14.

Females Only

Have you ever had a problem with...

15.

- a. Vaginal Dryness
- b. Vaginal stricture(narrowing)
- c. Vaginal Pain

	Prior to Ostomy	After Ostomy	Currently
a. Vaginal Dryness	 Yes  No	 Yes  No	 Yes  No
b. Vaginal stricture(narrowing)	 Yes  No	 Yes  No	 Yes  No
c. Vaginal Pain	 Yes  No	 Yes  No	 Yes  No

Males Only

Have you ever had a problem with...

	Prior to Ostomy	After Ostomy	Currently
a. Getting an Erection	 Yes  No	 Yes  No	 Yes  No
b. Maintaining an Erection	 Yes  No	 Yes  No	 Yes  No

Diet

16. In a typical day,
- a. how many meals other than snacks do you eat? _____
 - b. How many snacks do you eat? _____
 - c. How many 8 oz cups of liquid do you drink?
(Please count all beverages such as water, tea, coffee, soft drinks, and juices.
Do not include alcoholic beverages) _____
 - d. How many alcoholic beverages do you drink? (Please count all beer, wine, and liquor. Note: one drink is equal to one shot of liquor, 12 oz can or bottle of beer, or one glass of wine) _____

17. How would you describe your current diet? (Check all that apply)

- High protein, low carb
- Fast Foods
- Diabetic
- Vegetarian
- Vegan
- Heart Healthy
- No Special Diet
- Other _____

18. Because of your ostomy, have you adjusted your diet?

- Yes; No

19. How long after your ostomy surgery did you feel comfortable with what you eat?

- < 1 month;
- 1-12 months;
- >12 months;
- I am still not comfortable

Physical Activities

20. Considering a typical 7-day period (a week) in the past month, how many times on average did you do any of the following kinds of exercise for more than 15 minutes during your free time and for how long per exercise session (in minutes)?

Please write the number of **times per week** in the first box and the **average amount of time** for each exercise session in the second box. If you did no recreational activity in the past month, please put a zero (0) in the spaces provided. Please do not leave blanks.

- a. Strenuous Activity (heart beats rapidly, heavy sweating)
 ____ times per week ____ average minutes
- b. Moderate Activity (not exhausting, light sweating)
 ____ times per week ____ average minutes
- c. Mild Activity (minimal effort, no sweating)
 ____ times per week ____ average minutes
- d. How does the past 30 days of activity reflect your normal activities?
 More
 Less
 Same

Smoking

21. Which of the following best describes your smoking history?

- I am a current smoker → skip to question 23
- I have never smoked → skip to question 24
- I once was a smoker → please answer question 22, 24

22. If you used to smoke but have stopped when did you quit? _____ Year

23. If you are currently a smoker or have been a smoker in the past:

- a. How many cigarettes per day on average? _____
- b. How many total years of smoking: _____

24. Do you currently use other tobacco products (chewing tobacco, snuff, pipes, cigars, etc.)?

Yes; No

Demographics

25. What is the level of school you have completed? Did not complete high school
 Completed high school /GED
 Vocational/secretarial/business
 Some college
 College degree
 Some graduate school
 Completed graduate degree

26. What is your height? _____ Feet, _____ Inches

27. What is your current weight? _____ Pounds

28. What was your approximate weight at the time of your surgery? _____ Pounds

29. Is your ethnicity Hispanic, Latino, or Chicano? Yes
 No

30. What race do you consider yourself? White
 Black or African American
 American Indian or Alaska Native
 Asian
 Native Hawaiian or Other Pacific Islander
 Other
 More than one race (Please specify)

31. What is your current annual income of your household? <15,000
 15,000-30,000
 30,001-50,000
 50,001-75,000
 75,001-100,000
 greater than 100,000

32. What was your marital/partner status immediately prior to your ostomy? (please choose one)

Single; Married; Divorced; Widowed; Separated; Partnered

33. What is your marital/partner status now?

Single; Married; Divorced; Widowed; Separated; Partnered

34. If your marital status has changed, was it a result of your ostomy?

Yes
No

15.2 Appendix 2b COH-QOL-CRC (scaled items only)

Survey: City of Hope Quality of Life Colorectal Cancer (COH-QOL-CRC) scaled items

Subject ID

Today's Date (month/day/year) / /

Directions: We are interested in knowing how the experience of having an ostomy affects your quality of life. Please answer all of the following questions based on your life at this time.

Please **fill in** the bubble 0-10 that best describes your experiences. For example:
How difficult is it for you to **climb stairs**?

Not at all difficult **Extremely Difficult**

										
0	1	2	3	4	5	6	7	8	9	10

Filling the bubble "2" would mean you have some but not a lot of difficulty climbing stairs.

Related to your ostomy, to what extent are the following a problem for you at this time?

Quality of Life

Related to your ostomy, to what extent are the following a problem for you at this time?

1. Physical Strength

no problem		severe problem									
	0	1	2	3	4	5	6	7	8	9	10

2. Fatigue

no problem		severe problem									
	0	1	2	3	4	5	6	7	8	9	10

3. Skin Surrounding the Ostomy

no problem		severe problem									
	0	1	2	3	4	5	6	7	8	9	10

4. Sleep Disruptions

no problem		severe problem									
	0	1	2	3	4	5	6	7	8	9	10

5. Aches or Pains

no problem		severe problem									
	0	1	2	3	4	5	6	7	8	9	10

6. Gas

no problem		severe problem									
------------	--------------------------	--------------------------	--------------------------	--------------------------	--------------------------	--------------------------	--------------------------	--------------------------	--------------------------	--------------------------	----------------

29. Has your ostomy interfered with your **personal relationships**?

not at all completely

										
0	1	2	3	4	5	6	7	8	9	10

30. How much **isolation** is caused by your ostomy?

none a great deal

										
0	1	2	3	4	5	6	7	8	9	10

31. Is **support** from friends and family sufficient to meet your needs?

not at all extremely

										
0	1	2	3	4	5	6	7	8	9	10

32. Has your ostomy interfered with your **recreational/sports activities**?

not at all a great deal

										
0	1	2	3	4	5	6	7	8	9	10

33. Has your ostomy interfered with your **social activities**?

not at all a great deal

										
0	1	2	3	4	5	6	7	8	9	10

34. Has your ostomy interfered with your **ability to be intimate**?

not at all a great deal

										
0	1	2	3	4	5	6	7	8	9	10

35. Do you have enough **privacy at home** for doing your ostomy care?

not at all a great deal

										
0	1	2	3	4	5	6	7	8	9	10

36. Do you have enough **privacy when traveling** for conducting your ostomy care?

not at all a great deal

										
0	1	2	3	4	5	6	7	8	9	10

37. How much **uncertainty** do you feel about your future?

none at all extreme

										
0	1	2	3	4	5	6	7	8	9	10

38. Do you sense a **reason** for being alive?

not at all a great deal

										
0	1	2	3	4	5	6	7	8	9	10

39. Do you have a sense of **inner peace**?

not at all a great deal

										
0	1	2	3	4	5	6	7	8	9	10

40. How **hopeful** do you feel?

not at all

										
0	1	2	3	4	5	6	7	8	9	10

extremely

41. Is support you receive from **personal spiritual activities** such as prayer or meditation sufficient to meet your needs?

not at all

										
0	1	2	3	4	5	6	7	8	9	10

completely

42. Is support you receive from **religious activities** such as prayer or meditation sufficient to meet your needs?

not at all

										
0	1	2	3	4	5	6	7	8	9	10

completely

43. Has having an ostomy made **positive changes** in your life?

not at all

										
0	1	2	3	4	5	6	7	8	9	10

a great deal

